## **II. Background and Significance**

*Background* - Herpes zoster (HZ) is a frequently severe infection caused by varicella-zoster virus (VZV). 60% of the annual 1.2 million US cases occur in people  $\geq 50$  years of age, although immune compromise is another risk factor for HZ (1,2). Common to these two risk factors is a significant decline, to a critical level, of VZV T-cell mediated

immunity (VZV-CMI) initially stimulated by the primary VZV infection (childhood varicella) (3-5). Varicella also results in the lifelong persistence of VZV in sensory ganglia. Sporadic reactivation of VZV occurs, but such events typically remain subclinical because of VZV-CMI. However, when an adequate VZV-CMI response to reactivation is absent, propagation of VZV in the ganglion continues and spreads down the sensory nerve to cause the characteristic signs and pain of HZ (6). A live attenuated HZ vaccine (ZVL) has been available since 2006 to prevent this, but its efficacy for preventing HZ is 51% in the 1st 3y after immunizations and drops sharply after 5y, and efficacy decreases with the age of the vaccinee (7). Shingrix (RZV), a recombinant VZV glycoprotein E (gE) adjuvanted vaccine, which became available late in 2018, is remarkably superior, with 97% overall efficacy against HZ. RZV protection declines little over time (8). The efficacy of RZV is unique compared with any approved vaccines for older adults and any candidate vaccines for herpesviruses. The magnitude and persistence of RZV immunogenicity represent a paradigm shift in vaccinology that warrants granular studies.

**Significance** - Central to understanding the superiority of RZV is determining the timing, magnitude, and nature of the systemic and local immune events at the site of VZV reactivation and replication. *Since the milieu of sensory ganglia cannot be directly evaluated, this proposal will use intradermal (ID) administration of live attenuated VZV vaccine (vOka strain) to simulate reactivated VZV replication in the skin.*

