## C. Study Design and Research Methods

### **Part A; Cohorts 1 and 2**

Seventy subjects with documented evidence of a HZ vaccine at least 5 years previously, divided equally between recipients of ZVL (Cohort 1) or RZV (Cohort 2) - 35 in each group - will be enrolled. Participation will consist of 4 visits over the course of 7-10 days in which blood is drawn, a challenge dose of vOka is given, and a skin biopsy is obtained.

ID vOka challenge live attenuated VZV (as 1 dose of licensed ZVL; Zostavax) will be prepared by mixing 0.35 ml of accompanying diluent with the vaccine and injecting 2 side-by-side intradermal doses of 0.125ml each, for a total of 0.25 ml (about  $\frac{3}{4}$  of the normal dosage or 13,857 plaque forming units) intradermally in the non-dominant deltoid region, using a NanoPass MicronJet600 device, on D0. Blood (60 ml) will be drawn prior to vaccination (D0), and at Days 1, 3, and 7. A skin biopsy (4 mm punch biopsy) will be done at the injection site, on the first 20 subjects (up to 25, if replacements needed) in each vaccine group; five each of these 20 will be biopsied on Day 0, 1, 3, or 7 in the order in which the participants enter the study. The Day 0 biopsy will be done on the contralateral arm in the deltoid region prior to vaccination. Initially every subject enrolled will be required to do the biopsy; this is reflected in the consent. The consent form will be amended to remove references to the biopsy procedure once the number of subjects needed for the biopsies is reached.

Subjects in the ZVL group will be offered RZV vaccine (to comply with ACIP recommendations for shingles immunization), to be administered beginning  $\geq$  60 days after Day 0. If subject wishes to receive the RZV vaccine, 2 additional visits will be required at Day 60 and Day 120, increasing the duration of participation up to 4 months. Subjects will not be reimbursed for these visits but will receive the vaccine free of charge.

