##### For analysis of kinetics of DNAemia:

For sample size estimation, we assumed an incidence of viremia of 86% in the ZVL group and a  $\geq 2$ -fold reduction in the RZV group. The 2-fold reduction is a conservative estimate, considering that the efficacy is 2.9-fold higher 5y after RZV vs. ZVL. With 19 participants per group, we have 80% power to detect a 2-fold difference in viremia with  $\alpha=0.05$ . However, a larger sample size is needed to achieve the 2ary objectives. 35 participants per group will allow us to have sufficient power in correlation analyses of our primary outcome measure with 2 measures of the immune responses, which may represent clusters of several analytes that group together using PCA or other dimensionality reduction method. For the primary objective, logistic regression models will be fit using VZV DNAemia defined in Section 13.2. as a dependent variable and vaccine group as the primary independent variable and adjusted for potential confounders such as age at vaccination, age at ID vOka challenge, sex, and/or race as appropriate. For all regression models fit to the data, 95% confidence intervals will be reported based on Wald statistics in conjunction with appropriate asymptotic normal distributional theory. Secondary analyses will include the duration of DNAemia defined as the last day after ID vOka administration when the VZV DNA PCR

Relative change in percentages between groups	Total sample size (50% of total in ZVL group and 50% in SRX group)
50%	70
65%	60
80%	45
90%	25

was positive, the magnitude of VZV DNAemia, defined as the peak viral load, and the occurrence of VZV RNAemia defined as  $\geq 1$  VZV RT-RNA PCR positive result during the first week after the ID vOKA challenge.

For analysis of soluble factors and phenotypic markers:

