We will generate descriptive tables of response and compare soluble factors and phenotypic markers between the 2 groups using multivariate analysis methods. We will use Hotelling's T2 test for the flow cytometric and soluble factors. We will adjust the outcome measures for potential confounders and redo the T2 test. If necessary, outcome measures will be log-transformed in order to better satisfy the assumptions of the T2 method. Cross sectional pairwise comparisons of gene expression will be made at 0, 1, 3 and 7d between groups using the DESeq2 package. Genes differentially expressed at day 0 will be filtered out at subsequent time points to avoid confounders unrelated to the intervention. Differentially expressed genes of interest at 1, 3 or 7d will be validated by RT-qPCR and used as input for downstream gene ontology pathway analysis. We will use the lists from each time point to investigate trends in gene expression over time (e.g. Is gene A upregulated at all time points?). Due to the large number of tests, False discovery rate (FDR) will be controlled at the level of 0.05.

For analysis of soluble markers and relationship to transcriptomic results:

We will generate descriptive tables of vOka replication and immune responses from all parameters by vaccine groups. We will use generalized linear models (GLM) to identify correlates between local vOka replication and viremia and between local and systemic APC, NK and Tconv, soluble markers and gene expression. Correlations will be examined between biopsies and systemic data collected at the same, preceding, and following time points. We will adjust for age and gender as appropriate and use FDR p-values.

For analysis of systemic and local immune responses that limit viremia:

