With the different biological measurements, the major analytical goal will be to determine biomarkers that serve as intermediates in the pathway between virus challenge with DNAemia. With all the matched measurements (transcriptomic, soluble marker, VZV-CMI T cell responses) on the same subjects, we will use mediation analysis methods (15) in order to evaluate the mediation potential of these markers. As a primary analysis, we will create a composite mediation score based on the following linear combination:  $V_i = \sum_{m=1}^M \beta_m X_{mi}$ , where  $\beta_m$  denotes an association between molecule m with the exposure, and  $X_{mi}$  is the measurement on molecule m for subject i,  $i=1,\dots,n$ . Upon standardizing V, we then can test for mediation using the approach in Vittinghoff et al. (16). Based on the available  $n = 70$ , we performed power analyses based on the Vittinghoff et al. approach to evaluate power for mediation of the composite marker. We assumed that the probability of outcome is 56% based on our preliminary data and that we are testing at a significance level of 0.05. Using the powerMediation package in R (<https://cran.r-project.org/web/packages/powerMediation/index.html>), with the given sample size, we will have at least 80% power of identifying mediating effects of V that

are at least 1.96 on the log odds ratio scale based on the proposed extended Sobel test given in Vittinghoff et al. (16).

Sample size: Sample size is 70. Calculation for predictability of this sample size is described above.

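### The mediation analysis names no confounder; if age affects DNAemia other than through V, a score that only tracks age can pass as a mediator

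*Combined protocol and SAP*

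**What the plan says.** Hypothesis 3 in Section I is a mediation claim. The analysis that carries it is the last block of Section IV.G, on systemic and local immune responses that limit viremia. Each marker is weighted by its association with the exposure, the weighted markers are summed to V, and then: "Upon standardizing V, we then can test for mediation using the approach in" a cited paper. No age, sex, race or other covariate is named for the weights, for V or for the DNAemia model. The power statement has these inputs: "Sample size: Sample size is 70"; "We assumed that the probability of outcome is 56% based on our preliminary data"; "testing at a significance level of 0.05". It claims at least 80% power for a mediating effect of 1.96.

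Other blocks of the same section do provide for adjustment:

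- The primary logistic model is "adjusted for potential confounders such as age at vaccination, age at ID vOka challenge, sex, and/or race as appropriate".
- Hotelling's T2 test is run and then repeated with outcomes adjusted for potential confounders, which are not listed.
- The generalized linear models for correlates carry the sentence "We will adjust for age and gender as appropriate and use FDR p-values".

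Section II says of older age and immune compromise: "Common to these two risk factors is a significant decline, to a critical level, of VZV T-cell mediated" immunity. Eligibility starts at 50 years with no upper limit (Section IV.B), so age may vary widely.

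**The concern.** Whatever the comparability of the vaccine groups, nobody is assigned a level of V. The association of V with DNAemia within vaccine group is observational. The candidate markers include VZV-specific T-cell responses, which the plan itself expects to fall with age. If older participants also control vOka less well for reasons that V does not capture, a model with vaccine and V but without age credits V with the effect of age. Balance on age between vaccine groups does not prevent this, because age here confounds the mediator-outcome path and not the vaccine-outcome path. Age imbalance is possible as well, since Part A enrols people by the vaccine they received at least 5 years earlier: "divided equally between recipients of ZVL (Cohort 1) or RZV (Cohort 2) - 35 in each group".

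At stake is the conclusion on Hypothesis 3: a shared age trend could be reported as the mechanism by which RZV protects.

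**Working it through.** **1. The plan's own figure.** Inputs from Section IV.G: n = 70, outcome probability p = 0.56, alpha = 0.05, power 80%. The formula is not printed in the plan. I assume the usual Wald form for a logistic coefficient of a standardized V, where R2 is the share of the variance of V explained by the other terms in the model:

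b = (z[1-alpha/2] + z[power]) / sqrt(n p (1-p)(1-R2))

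With two-sided alpha and R2 = 0: b = (1.960 + 0.842) / sqrt(70 x 0.56 x 0.44) = 2.802 / 4.153 = 0.675, and exp(0.675) = 1.96. The stated 1.96 therefore reproduces as an odds ratio (the plan labels it a log odds ratio), and only with R2 = 0. Under this formula, no covariate was budgeted, and neither was any correlation between V and vaccine.

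**2. False-positive rate, single marker.** Simulated trials of 35 + 35, with DNAemia 86% after ZVL and 43% after RZV (the sample-size assumptions in Section IV.G). Assumed: vaccine-marker correlation 0.5, no marker effect on DNAemia, groups balanced on age. The documents give none of the age effects. There were 3,000 trials per setting.

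| Age-marker correlation | Age log OR per SD | V path significant, without / with age | Sobel test, without / with age | Spurious log OR per SD |
|---|---|---|---|---|
| 0 | 0.7 | 4.0% / 4.6% | 2.0% / 2.2% | about 0 |
| -0.3 | 0.4 | 7.3% / 4.9% | 3.8% / 2.9% | -0.16 |
| -0.3 | 0.7 | 10.6% / 4.1% | 6.7% / 2.5% | -0.27 |
| -0.5 | 0.7 | 24.8% / 5.0% | 17.7% / 3.3% | -0.46 |
| -0.5 | 1.0 | 38.8% / 4.6% | 28.9% / 3.4% | -0.61 |

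**3. False-positive rate, composite.** The plan tests one weighted score, not single markers. For a composite of 20 such markers, the Sobel rate without age was about 19% at -0.3 and 0.4, rising to about 84% at -0.5 and 1.0. With age it was 4% to 5%.

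A second simulation used markers with no vaccine effect of their own, correlation with age of 0.3 to 0.7 and an age odds ratio of 1.5 to 3 per SD (1,500 trials per setting). The V path was significant in 8.4% to 76.9% of trials with balanced groups, and in 11.9% to 90.1% with a 0.5 SD age difference. With age in the DNAemia model the range over both was 3.9% to 5.2%. With no age-marker correlation it stayed near 5%.

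The composite fares worse because summing cancels the markers' independent noise and keeps what they share. In these simulations that is only vaccine and age. Markers with other shared variation would give a smaller inflation.

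**4. Cost of adjustment.** Same formula, with R2 of V on vaccine and covariates assumed:

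| R2 | Detectable OR at 80% power | Power at OR 1.96 |
|---|---|---|
| 0 | 1.96 | 79.8% |
| 0.1 | 2.04 | 75.5% |
| 0.2 | 2.13 | 70.5% |
| 0.3 | 2.24 | 64.7% |
| 0.5 | 2.60 | 50.6% |

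Part of this loss is not due to age. If V and vaccine correlate at 0.5, R2 is already 0.5^2 = 0.25 and power at OR 1.96 is 68%. Adding age with correlation 0.3 to 0.5 raises R2 to 0.25 + 0.09 = 0.34 or 0.25 + 0.25 = 0.50, and power falls to 62% or 51%.

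**The case against.** The strongest objection is causal. Section II says that age lowers VZV T-cell immunity and that inadequate immunity lets zoster develop. On that account age acts through immunity. No section reports an effect of age on vOka DNAemia by another route. If all of it runs through V, the unadjusted coefficient is not biased by age and adjustment only costs power. In a simulation of that case (true log OR -0.9 per SD, age-marker correlation -0.5, no direct age effect), the median estimate was -0.95 unadjusted and -0.94 adjusted, and Sobel power was 63% against 47%. This stands, and it makes the finding conditional. It does not justify leaving age out: a score from selected blood and skin measurements is unlikely to capture everything about ageing that bears on viral control, and the plan treats age as a potential confounder of the same outcome in its primary model.

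It also stands that the mildest single-marker setting shows no material inflation: two separate runs gave 6.2% and 7.3% for the path, and 4.1% and 3.8% for Sobel. That does not carry over to the composite, which is what the plan tests.

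A reader might infer three stronger things that the documents do not support:

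- That this is the only analysis without a confounder. The DESeq2 comparisons (day 0 gene filter only), the secondary DNAemia outcomes and the correlation analyses that justify 35 per group name none either.
- That every other analysis is firmly adjusted for age and sex. The primary and correlate models say as appropriate, and the T2 confounders are not listed.
- That the plan excludes covariates. It prints no regression equation and refers to a cited method, so the accurate statement is that none is named.

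**Conclusion.** The point holds in conditional form. The mediation block names no confounder at any of its three steps, although the plan provides for adjustment elsewhere and itself links age to VZV immunity. If age affects DNAemia by any route outside V, the test of V exceeds its nominal 5%, with or without age balance between groups. Over the assumed age effects this runs from negligible for a single marker under weak effects to most trials for a many-marker composite under strong ones. The direction is secure under that condition; the size is not, because the documents give neither the age effects nor the correlations among markers. The false conclusion would be chiefly that V mediates, not a list of individually false markers. This should be changed before analysis. It improves a secondary-objective analysis and does not touch the primary comparison.

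**What to change.** In the mediation block of Section IV.G, prespecify age at ID vOka challenge and sex, both already named for the primary model, as covariates in (a) the marker-exposure associations used as weights, (b) the model for V, and (c) the DNAemia model that contains vaccine and V. Report the unadjusted analysis as a sensitivity analysis. Step (c) restored the error rate in the second composite simulation even with unadjusted weights; step (a) keeps an age difference between vaccine groups from shaping V itself.

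Restate the mediation power with a stated R2 of V on vaccine and covariates, and say whether 1.96 is an odds ratio or a log odds ratio.

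The change needs SAP wording only and no new data. The price is stated power: at n = 70 and an assumed R2 of 0.1 to 0.5, power at an odds ratio of 1.96 is about 76% to 51% instead of 80%. Part of that is owed in any case, because the R2 = 0 behind the present figure leaves out the correlation of V with vaccine.

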#### **H. Summarize Knowledge to be Gained**

This project is designed to determine why RZV is a superior vaccine compared to ZVL, and to understand why it is uniquely effective in protecting elderly people. This will be accomplished by understanding the timing, magnitude, and nature of the systemic and local immune events at the site of VZV reactivation and replication. *Since the milieu of sensory ganglia cannot be directly evaluated, this proposal will create a model for this purpose, which will be intradermal administration of live attenuated VZV vaccine (vOka) strain to simulate reactivated VZV replication in the skin.* Both systemic and local responses to this challenge will be determined. Understanding how a vaccine for older people successfully limits a common infection (namely HZ) in ageing individuals may be applicable to the general problem of improving the immunogenicity of other vaccines for older people.

#### **I. Future Studies**

Serum plasma and white blood cells will be archived for future studies of immune responses to VZV.

